#### **4.5.2.2 Derivation or calculation of endpoint**

For each dimension in QOLRAD and GSRS respectively, the average score will be calculated. Dimensions for the respective questionnaires are defined in the previous Section. The procedure adopted to handle missing values in questionnaires is defined in Section [6.2.1](#).

## **5. DATA MANAGEMENT**

The AstraZeneca monitor will continuously check and collect all CRFs. Corrections or additions in the CRFs must be initialled and dated by qualified study personnel. Any remaining questions or missing data will be noted on Data Clarification Forms (DCFs), which will be sent to the investigator. It is the investigator's obligation to complete and return them to AstraZeneca as soon as possible.

Data Management at AstraZeneca in each respective country will perform data entry and validation continuously and promptly during the study. The data will be entered into an Oracle database using RAMOS as the data entry application. When data have been entered into the database, proof reading will be performed to ensure that the entered data are correct and complete according to the CRF.

Adverse events will be classified according to the terminology of the MedRA. Concomitant medication will be classified according to the WHO Drug Dictionary and the Anatomical Therapeutic system (ATC).

It is the responsibility of the investigator to complete Serious Adverse Event Forms (part of the CRF) when applicable. It is the AstraZeneca monitor's responsibility to ensure that any Serious Adverse Event Form is completed.

All data editing and data validation activities will be performed by investigators, monitors and data management staff. All data editing and data validation procedures have to be carried out

and the AstraZeneca “clean file” procedure have to be completed. Clean file is defined as a status where the data in the CRFs, the database and the reference values are complete and logical according to the study protocol, general guidelines and data entry instructions. The contents of the database must correspond to that of the CRF together with Data Edit Documents, DQFs, general guidelines and data entry instructions.

### **Reporting of genotypic results**

Results from any genetic research performed will be reported separately from the clinical study report. AstraZeneca will not provide individual genotype results to subjects, their family members, any insurance company, an employer, clinical study investigator, general physician or any other third party, unless required to do so by law. The subject’s DNA will not be used for any purpose other than those described in the study protocol.

Individual subjects will not be identified in any report or publication resulting from this work. The data and results of this study may be reviewed with collaborators and published, but neither the subject’s name nor any other personal identifiers will appear in any publication or report.

## **6. STATISTICAL METHODS AND DETERMINATION OF SAMPLE SIZE**

### **6.1 Determination of sample size**

The true rate of treatment successes (i.e. subjects who have not experienced treatment insufficiency within 5 years) is assumed to be at least 70% for both treatments. With 275 subjects on each treatment the true difference between treatment is, with a probability of 95%, not going to differ by more than 8 percentage points from the observed difference.

### **6.2 Statistical evaluation**

#### **6.2.1 Methods of statistical analysis**

A comprehensive Statistical Analysis Plan will be prepared before unblinding the data, or in instances where the data are not blinded, database lock.

Both Intention To Treat (ITT) and Per Protocol (PP) analyses will be made for the primary variable. Secondary variables will be analysed for the ITT population only. In the ITT analyses all randomized subjects will be included, except subjects who are randomized into medical treatment and who have taken no dose of study drug, or subjects who are randomized to laparoscopic fundoplication and who refuse to undergo the operation. The PP population will include subjects with no major protocol violations, including the violation of entry criteria (the nature and reasons for these protocol violations will be defined and documented before

database lock). Subjects eligible for safety evaluation are those who take at least one dose of the study drug and for whom post-dose information is available.

The two treatment groups will be compared regarding the primary endpoint using Life Table methods for graphic presentation and a logrank test for statistical inference.

For each GSRS and QOLRAD dimension, the individual score at each assessment is calculated as the average score for the items included in the dimension. If there are missing items in the questionnaires, the mean of the completed items in one dimension will be imputed to substitute the missing item provided that more than 50% of the items in one dimension are completed.

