**Statistical methods**

The treatment arms will be compared regarding time to evidence of treatment failure by a logrank test. The comparison will be made for an ITT population.

Other endpoints will be analysed descriptively.

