**Subjects untreated with PPI prior to study start will (if possible):**

- (i) start the run-in period with the “investigational week” at visit 1. In such cases an endoscopy with biopsy sampling will be made at visit 1. If insufficient biopsies have been taken at visit 1 then another endoscopy with biopsy sampling will be done at visit 3. In cases of mucosal breaks classified as LA grade C or D at visit 1 or 3 a new endoscopy must be performed at visit 4 prior to randomization. Furthermore, laboratory measurements, 24 hr pH metry, manometry and SAP will be made. If these assessments can be made within 2 weeks from visit 1 then visit 2 and 3 can be left out. The study drug (esomeprazole 40 mg o.d.) will then be dispensed and the subject will continue the run-in period. If the time between first endoscopy (visit 1) and the 24 hour pH metry is more than 2 weeks, the study drug must be dispensed at visit 1 and the subject will follow the same routine as the **treated subject (i)**.

10-year study period

If reflux esophagitis LA grade C or D is found at visit 3, a new endoscopy must be done at visit 4 prior to randomization.

- Subjects will be randomized to either medical treatment or surgery at visit 4. Medical treatment is 20 mg o.d. (start dose) and can be adjusted, but is not to exceed 40 mg daily. Surgery must be performed within 3 months after randomization. The subject is allowed to be treated with esomeprazole 20 mg o.d. and can be adjusted, but is not to exceed 40 mg daily whilst awaiting the surgery. Visit 5 and 6 will only be attended by subjects randomized to surgery.
- Endoscopy with biopsy sampling will be performed at visit 8, 12, 16, 33 and 39. A 24 hour pH metry and SAP will be performed at visit 7 and 16. Endoscopy will be performed at extra visits in case of symptomatic relapse or early discontinuation. A 24 hr pH metry and SAP should be performed in case of dose adjustments (prior to).
- Symptoms will be assessed at each visit except at visit 5 and the telephone visits (visit 30, 32, 34, 36, 38). Laboratory screen will be done at visit 8, 12, 16, 33 and 39 and at early discontinuation visits.
- Patient reported outcomes (PRO) will be assessed by QOLRAD and GSRS at visits 4, 8, 10, 12, 14, 16, 31, 33, 35, 37 and 39 and at early discontinuation visits.
- Body weight will be assessed at visits 4, 8, 12, 16, 33, 39 and at extra visits and at early discontinuation visits.

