#### **3.3.5.3 Incorrectly enrolled or randomized subjects**

Incorrectly enrolled or randomized subjects will be discontinued from further study treatment and assessments.

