### **3.4.4 Blinding and procedures for breaking the blind**

#### **3.4.4.1 Methods for ensuring blinding**

Not applicable, as this is an open study. See Section [3.2](#).

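### The population labelled ITT drops randomised subjects who refuse surgery or take no dose, so the primary comparison is not of the groups as randomised

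*Protocol*

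**What the plan says.** The synopsis, under Statistical methods, names the primary population: "The comparison will be made for an ITT population". Table 3 repeats this for time to treatment failure, and Section 6.2.3 applies a two-sided logrank test.

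Section 6.2.1 defines the set: "In the ITT analyses all randomized subjects will be included, except" for two groups. One is "subjects who are randomized into medical treatment and who have taken no dose of study drug"; the other is "subjects who are randomized to laparoscopic fundoplication and who refuse to undergo the operation". The same section says "Both Intention To Treat (ITT) and Per Protocol (PP) analyses will be made for the primary variable", and restricts the per-protocol set to subjects without major violations. Secondary variables use the ITT set only.

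Four other provisions bear on this:
- On blinding, Section 3.4.4.1 says "Not applicable, as this is an open study".
- Section 3.1 says "Surgery must be performed within 3 months after randomization". Esomeprazole is provided for during the wait (Sections 3.1, 3.4.2 and 3.4.5).
- Section 4.3.2.1 counts days from the start of treatment after randomisation, not from randomisation.
- Section 6.2.3 censors subjects who discontinue for any reason other than treatment failure.

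**The concern.** A set that loses subjects because of decisions taken after randomisation, with the allocation known, is not intention-to-treat. Randomisation no longer guarantees that the two groups are alike, and the logrank test relies on that.

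The two exclusions are also unequal in kind. A medical-arm subject has just completed a 12-week run-in on esomeprazole and is lost only by taking no dose, which is likely to be rare. It is rarer still if run-in tablets count, since Section 3.1 calls the run-in esomeprazole the study drug. A surgical-arm subject has up to three months in which to decline an operation. That subject has already responded to esomeprazole in the run-in, had no more than mild symptoms at randomisation, and may still be taking the drug. The test would then set nearly everyone allocated to drug against those allocated to surgery who did not refuse it. This is the trial's only formal efficacy test, and the same set carries into the secondary tables.

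**Working it through.** **Inputs from the protocol (Section 6.1).** 275 subjects per arm; 5-year success of at least 70% in both arms; 95% confidence; stated precision of 8 points for the difference.

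**Inputs assumed.** The refusal fraction x in the surgical arm is taken as 5-15% (14 to 41 of 275). The gap between the 5-year success of the subjects kept and that of refusers is taken as 10-30 points. Medical-arm exclusions are taken as nil.

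**1. The plan's own figure.** Half-width = 1.96 × √(2 × 0.70 × 0.30 / 275) = 0.0766, or 7.66 points. The stated 8 points reproduces as a rounded upper bound, so the sample-size statement is sound.

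**2. Shift caused by the exclusion.** Let R be the success rate in all subjects randomised to surgery, S the rate in those kept, and q the rate in refusers. Then R = (1 − x)S + xq, so S − R = x(S − q).

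| Refusal x | gap 10 points | gap 20 points | gap 30 points |
|---|---|---|---|
| 5% | 0.5 | 1.0 | 1.5 |
| 10% | 1.0 | 2.0 | 3.0 |
| 15% | 1.5 | 3.0 | 4.5 |

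The sign follows S − q, which the protocol does not settle. With S = q the shift is zero.

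**3. Effect on the test when the arms are truly equal.** Set R = 70% in both arms, and take q = 50% or 90%. Then S = (0.70 − xq)/(1 − x). For x = 10% and q = 50%, S = 0.65/0.90 = 72.2%, a shift of 2.2 points. Type I error is taken from a two-sided 5% comparison of proportions, standing in for the logrank test.

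| Refusal x | shift (points, either sign) | type I error |
|---|---|---|
| 5% | 1.05 | 0.058 |
| 10% | 2.22 | 0.085-0.087 |
| 15% | 3.53 | 0.136-0.143 |

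With q = 60% or 80% and x = 10%, the shift is 1.1 points and the type I error 0.059.

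**4. Effect on precision.** If 5%, 10% or 15% of the surgical arm is dropped (261, 248 or 234 left), the half-width becomes 7.76, 7.87 or 7.99 points. It stays within the stated 8 points throughout, so the precision statement gives no warning of the bias.

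**5. Whether another provision restores these subjects.** The protocol names only one other population for the primary variable, and it is narrower. A refuser also has no start of treatment under Section 4.3.2.1, so changing the population without changing the time origin would leave that subject's time undefined.

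**The case against.** The best defence is that refusals may be few. Section 3.1 admits only subjects willing to accept randomisation to either treatment, and the entry criteria require suitability for both. At 5% refusal and a 10-point gap the shift is half a point. Both inputs are assumptions, and the upper value of 4.5 points needs both extremes together. That refusers are people who did well on the drug while waiting is a plausible mechanism, not a documented one. All of this stands and limits the size of the point. It does not make the set intention-to-treat, and the protocol neither estimates nor caps refusal.

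A reader might go further in four ways that the document does not support:
- **That 3.5-10.5 points are at stake.** Counting every refusal as a failure turns 70% into 0.70 × (1 − x), or 66.5% to 59.5%. The endpoint does not define refusal as failure, so this measures a different endpoint and not the bias from exclusion. Nor is the 8-point precision of a difference a tolerance for a shift in one arm.
- **That Section 3.3.5.3 removes more subjects.** It says "Incorrectly enrolled or randomized subjects will be discontinued from further study treatment and assessments". That ends treatment and assessment; it takes nobody out of the ITT set.
- **That the surgical result covers operated subjects only.** Subjects left unoperated for reasons other than refusal remain in the set.
- **That no all-randomised analysis exists.** Section 6.2.1 announces a statistical analysis plan, which is not available here and may contain one. The criticism is of the primary population that the protocol fixes.

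**Conclusion.** The point holds as an error in the definition and label of the primary population. As written, the rule permits unequal selection after an open allocation, and the primary logrank test is not a comparison of the groups as randomised.

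The size is uncertain and may be small: about 0.5-4.5 points in the surgical-arm 5-year rate if 5-15% refuse and the outcome gap is 10-30 points, and nil if refusers resemble the rest. The direction is unknown, so it cannot be said that the rule favours surgery or esomeprazole. The sample-size statement is unaffected.

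**What to change.** - **Section 6.2.1:** define the primary population as all randomised subjects, analysed in their allocated arm. Rename the present set modified ITT and keep it as a supportive analysis. Align the synopsis and Table 3.
- **Section 4.3.2.1:** start the clock at randomisation in both arms.
- **Section 6.2.3:** state that refusers stay in the analysis and, if they discontinue without failure, are censored at their last available assessment.
- **Sensitivity analyses:** vary refusers' outcomes, including one analysis that counts refusal as failure. Use the 5- and 10-year telephone follow-up of Section 3.1 where available. These are needed because a refuser censored within the first months adds little to the logrank test.
- **Operative tables:** keep operated subjects as the denominator for per- and post-operative events.

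The medical-arm failure questions contain dose steps. Carrying them over to unoperated surgical-arm subjects would set clinical management and is not proposed.

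The planned sample size need not change: 275 per arm gives the 7.66-point half-width. The direct cost is wording, one more run of the primary analysis and the sensitivity runs. Non-compliance will dilute the contrast somewhat. Data on refusers will be limited: the calls record GERD surgery, present treatment and present symptoms at two time points, and they miss subjects who withdrew consent. Timing also matters. Last subject in was planned for Q4 2002, so the 3-year interim analysis falls around the end of 2005, before the prolongation starts in Q1 2007. A change made after that look should be dated, justified and settled before database lock, with both populations reported.

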### 3. STUDY PLAN AND PROCEDURES

#### 3.1 Overall study design and flow chart

This study is designed as a 5-year, randomized, open, parallel-group multicentre trial with a 5-year prolongation with the objectives to estimate the efficacy and tolerability of esomeprazole compared with anti-reflux surgery, in a long-term treatment of adult subjects with confirmed, symptomatic gastroesophageal reflux disease with or without esophagitis (objectively documented by endoscopy and abnormal 24 hour pH metry). All subjects should be eligible for surgery.

The study will begin with a 12-week run-in period enabling the recording of baseline values and responses to medical treatment with esomeprazole 40 mg o.d. This period will end with a randomization into the 10-year study period. All subjects should have the need for continuous treatment to control reflux and be eligible for anti-reflux surgery. Subjects should not have more than LA grade B endoscopic-visualized mucosal breaks or more than mild symptoms of GERD prior randomization and should have responded to esomeprazole treatment in the 12-week run-in period.

The 10-year study period consists of 2 treatment arms, medical treatment (esomeprazole, start dose is 20 mg o.d.) and anti-reflux surgery (laparoscopic fundoplication). Subjects willing to accept randomization to either surgery or long-term medical treatment will receive treatment according to a randomization list.

*Helicobacter pylori* (*Hp*) status will be assessed based on biopsy material.

In case of confirmed peptic ulcer disease and positive *Hp* testing eradication therapy should be given prior to enrolment. Subject should not be enrolled within 3 months after therapy.

In case of a first episode of peptic ulcer disease during the 10-year study period and confirmed positive *Hp* testing eradication therapy is allowed.

In all other cases of *Hp* infection not associated with peptic ulcer disease eradication therapy is not allowed.

The planned number of subjects is 550 randomized in 11 countries, with at least 6 subjects per centre.

Visits 1, 2, 3, 4, 5, 6, 7, 8, 12, 16, 31, 33, 35, 37 and 39 will be regular visits with the investigator and visits 9, 10, 11, 13, 14 and 15 may be done by the study nurse.

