### **3.4.2 Doses and treatment regimens**

The medication arm of the study design includes the following:

- esomeprazole
- oral administration
- the start dose is 20 mg once daily and may be adjusted not to exceed 40 mg total daily dose and be swallowed together with a glass of water.

The surgical arm of the study design includes the following:

The surgical procedure is laparoscopic fundoplication. The surgical procedure to be used is laparoscopic total fundoplication and reconstruction of the hiatus. A per-operative record should be filled in and sent by the monitor to AstraZeneca R&D Mölndal for datahandling. The procedure should be done by or supervised by an experienced surgeon. Surgery should be performed within three months of randomization. The subject is allowed to be treated with esomeprazole 20 mg o.d or 40 mg o.d awaiting the surgery.

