**Table 4 Safety objectives and endpoints relating to each objective**

Objective	Endpoints	Summary statistic for analysis (including timepoint and population)	Planned analysis	Significance of results
4.4.3 Laboratory screen variables	Laboratory assessments	
 
- Descriptive presentation of laboratory results for each sample occasion.
 
- Number of subjects with values below, within and above the reference range, over time.
 
- Median changes between baseline and the last visit for each laboratory variable.
 
- Graphs showing last visit values versus the baseline values for each laboratory variable.
 
-All clinical laboratory presentations will be made for the safety population.
 
	No formal statistical comparison.	The result will contribute to the determination of the adverse drug reaction pattern and frequency during long-term treatment with esomeprazole.
4.4.2 SAE and AE	Occurrence and nature (seriousness intensity and action taken to study drug due to AE) of all SAEs and AEs causing premature discontinuation of study drug and /or study.	
 
-Frequency of subjects with SAEs and AEs leading to discontinuation of study drug and/or study.
 
-AE pattern (e.g. by system organ classification)
 
- SAEs and discontinuations due to AE will be presented for the safety population
 
	No formal statistical comparison.	The result will contribute to the determination of the adverse drug reaction pattern and frequency during long-term treatment with esomeprazole.

The methods for collecting safety data are described below

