## **Serious Adverse Event**

A serious adverse event is an AE occurring during any study phase (i.e., run-in, treatment, washout, follow-up), and at any dose of the investigational product, comparator or placebo, that fulfils one or more of the following criteria:

- results in death
- is immediately life-threatening
- requires in-subject hospitalization or prolongation of existing hospitalization
- results in persistent or significant disability or incapacity
- is a congenital abnormality or birth defect
- is an important medical event that may jeopardize the subject or may require medical intervention to prevent one of the outcomes listed above

The causality of SAEs (i.e., their relationship to study treatment) will be assessed by the investigator(s), who in completing the relevant case report form must answer “yes” or “no” to the question “Do you consider that there is a reasonable possibility that the event may have been caused by the drug?” For further guidance on the definition of a SAE and a guide to the interpretation of the causality question, see Appendix F.

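### The safety population is defined by esomeprazole intake in both arms, so the surgical-arm SAE, AE-discontinuation and laboratory tables do not rest on the operated subjects

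*Protocol*

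**What the plan says.** Section 6.2.1 of the protocol defines the safety set once, for both arms: "Subjects eligible for safety evaluation are those who take at least one dose of the study drug", with the added condition that post-dose information exists. The same paragraph defines the ITT set arm by arm. It removes medical-arm subjects who took no study drug and, in the other arm, "subjects who are randomized to laparoscopic fundoplication and who refuse to undergo the operation".

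Table 4 uses the safety set for the adverse event results ("SAEs and discontinuations due to AE will be presented for the safety population") and for all laboratory presentations.

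Three other places bear on who has taken study drug:

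- Section 3.1 gives every subject a 12-week run-in to record baseline values and "responses to medical treatment with esomeprazole 40 mg o.d. This period will end with a randomization into the 10-year study period".
- The run-in text for subjects not previously on a PPI calls this treatment study drug: "The study drug (esomeprazole 40 mg o.d.) will then be dispensed". Table 1 also has study drug dispensed at visit 1.
- Section 3.4.2 covers the wait for surgery: "The subject is allowed to be treated with esomeprazole 20 mg o.d or 40 mg o.d awaiting the surgery". Section 3.1 likewise words this as permission, whereas section 3.4.5 words it as something that should happen.

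**The concern.** In a trial of a drug against an operation, a safety table for the surgical arm should describe people who had the operation. Here entry to the table depends on the other arm's treatment. The ITT rule in the same paragraph shows that an arm-specific definition was available, but it was not carried over to safety.

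Tolerability of esomeprazole compared with surgery is part of the stated aim (section 3.1). The dedicated operative tables cover the operation and roughly the first 30 days, and they have no medical-arm counterpart. Surgical-arm SAEs after that window, over up to ten years, and any side-by-side reading of SAEs between arms rest on the safety-population tables. If the surgical denominator there is not the operated subjects, the surgical rates are wrong for that purpose.

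**Working it through.** The protocol gives no figure for the size of the safety set or for the number of surgical-arm subjects not operated on, so there is no stated figure to reproduce. The check is a reading of the rule, followed by an illustration.

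**Step 1: the two readings of study drug**

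| | Run-in doses count | Only post-randomisation doses count |
|---|---|---|
| Support in the protocol | Run-in esomeprazole is named study drug (section 3.1); SAEs are recorded from visit 2, before randomisation (section 4.4.2.2) | The ITT exclusion of medical-arm subjects with no dose would remove almost nobody if run-in doses counted |
| Operated, no esomeprazole after randomisation | In | Out |
| Allocated to surgery, never operated, took esomeprazole while waiting | In | In |
| Allocated to surgery, never operated, no esomeprazole after randomisation | In | Out |
| Took run-in drug, never randomised | In (belongs to no arm) | Out |

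Neither column selects the operated subjects. In the second column, membership can also come from esomeprazole after surgery: section 3.4.5 lets the investigator dispense one bottle for on-demand use up to visit 7. Entry to the set could then depend on post-operative symptoms.

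**Step 2: size if run-in doses count**

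Inputs: 275 subjects per arm (section 6.1); share of the surgical arm not operated on, *r* (assumed); SAE rate due to the operation among operated subjects, *q* (assumed). Unoperated subjects cannot have an operative SAE, so

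tabulated rate = *q* × (1 − *r*).

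| *r* | Unoperated of 275 | *q* = 5% shown as | *q* = 10% shown as |
|---|---|---|---|
| 0% | 0 | 5.0% | 10.0% |
| 10% | 27.5 | 5.0 × 0.90 = 4.5% | 9.0% |
| 15% | 41.25 | 5.0 × 0.85 = 4.25% | 8.5% |
| 20% | 55 | 5.0 × 0.80 = 4.0% | 8.0% |

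The shift is always downwards and is zero if everyone allocated to surgery is operated on. It applies to the operative component of the SAE rate; unoperated subjects can still contribute unrelated SAEs.

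**Step 3: size if only post-randomisation doses count**

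If a share *s* of operated subjects takes no esomeprazole after randomisation (assumed), 275 × *s* subjects leave the set when all 275 are operated on: none at 0%, 27.5 at 10%, 68.75 (about 69) at 25%. Their events and their place in the denominator go together, so the direction of any bias depends on who they are and cannot be settled from the protocol.

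**The case against.** The other side has four good arguments.

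- **Operative harm has its own route.** Per-operative events and post-operative complications have their own assessments (sections 4.3.6 and 4.3.7). Table 3 places them on the ITT set among subjects randomised to surgery, and section 6.2.3 adds first-month descriptive tables. That ITT set excludes refusers, so it is close to the operated set. Deaths during surgery or in the following 30 days also count as treatment failures (section 4.1). All of this stands. A reader might infer that operative harm disappears from the report; the documents do not support that. Histology, too, is shown on the ITT set as well as the safety set (Table 3).
- **The literal reading keeps operated subjects in.** Run-in drug is called study drug, and section 3.4.5 says esomeprazole should be given before surgery. Exclusion of operated subjects is therefore conditional on the second reading. This stands, but the same literal reading brings in unoperated subjects.
- **The tables are descriptive.** Table 4 plans no formal comparison and directs the results to the adverse reaction profile of esomeprazole. This limits the consequence; it does not make the surgical denominator right.
- **The SAP can settle details.** That holds for table layout and listings. The definition itself, however, is written into the protocol, so it is a rule badly fixed rather than a detail left open.

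A reader might also object that the causality question asks only about the drug ("Do you consider that there is a reasonable possibility that the event may have been caused by the drug"). That changes no planned table: section 4.4.2.3 requires all SAEs to be reported whatever their cause, and Table 4 summarises frequency and pattern, not relatedness.

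**Conclusion.** The point holds as a modest denominator error. The stated rule does not give the operated subjects under either meaning of study drug. The surgical-arm SAE, AE-discontinuation and laboratory tables inherit this, including SAEs after the 30-day operative tables end. The primary endpoint, the operative tables and the ITT histology tables are unaffected. Subjects who were never randomised would enter the overall safety set on the literal reading, but they belong to no arm and do not alter the surgical denominator.

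The size is not known from the protocol. The illustrative fall from 5% to between 4.5% and 4.25% rests on two assumptions, a 5% operative SAE rate and 10% to 15% of the arm unoperated; neither is in the document. The stronger conclusion, that operated subjects and their events fall out of the safety tables, needs the further assumption that only post-randomisation doses count. The protocol does not say so.

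**What to change.** Replace the safety definition in section 6.2.1 with one based on treatment received:

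- medical arm: randomised subjects who took at least one dose of esomeprazole after randomisation;
- surgical arm: randomised subjects in whom the operation was started.

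List surgical-arm subjects who were not operated on separately, and report run-in events separately, including those in subjects never randomised. Carry the same definition into the SAP and the Table 4 outputs.

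The passages on esomeprazole before surgery (sections 3.1, 3.4.2 and 3.4.5) differ between permission and expectation and must be reconciled. With the definition above, the surgical safety set no longer depends on how that is resolved.

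The cost is a wording change in the protocol and SAP. Surgery, study drug dispensing and SAEs are already recorded, so no new assessments are needed.
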